1. VERSION HISTORY

Table 1. Summary of Changes

Version/ Date	Associated Protocol Amendment	Rationale	Specific Changes
1.0 02 Mar 2020	Original 27 Nov 2019 PACL 11 Feb 2020	N/A	N/A
2.0 26 May 2021	Amendment 1 08 Feb 2021	Protocol amendment	
 Updated verbatim protocol wording throughout Removed DXA throughout, as per protocol Updated wording throughout to reflect removal of CCI [REDACTED] PROs in Cohort 2 Updated all timepoints to reflect new SoA ‘Free’ replaced with ‘unbound’ throughout for both PK and PD endpoints Sections 3.1.3 and 3.1.4: Removed max. vitals decrease/increase over first 12 weeks, as not required Section 3.2 and 3.3: Additional wording added for clarification Section 3.3.2: Calculations included for change from baseline, relative change from baseline, duration of suppression, maximum concentration and time to maximum concentration Section 3.3.4: Wording simplified [REDACTED] Section 6.2: Added/removed some PK outputs Section 6.3.1: Added/removed some immunogenicity outputs Section 6.3.2: Additional wording added for clarification; Added some additional outputs; Analysis added for relative change from baseline GDF-15 Section 6.3.3: Additional wording added for clarification Section 6.3.4: Wording simplified Section 6.3.5: Wording simplified Section 7.2: Added further wording to describe interim analysis Appendix 2: Added additional wording for immunogenicity terms
3 21 Oct 2021	Amendment 1 08 Feb 2021	Requirement for additional output for POM declaration Findings during BDRs	
 Updated protocol title to match amendment 1 Sections 3.2 and 6.2: Added clarification for C_{trough} Sections 3.3.2 and 6.3.2: Added percent change from baseline; Changed summaries to be based on percent change from baseline. Removed duration of suppression of GDF-15 and reference to Emax and Tmax.

			
 Sections 3.3.3 and 6.3.4: Added percent change from baseline for body weight Section 6.1.1: Replaced ‘severity’ with ‘grade’ in description of TEAE table in second paragraph Sections 6.1.3 and 6.1.4: Combined individual and mean plots Section 6.1.4: Corrected endpoint for >500msec listing (QT rather than QTcF) Section 6.2: Added individual concentrations (and removed quartiles/sd) to median and mean trough concentration plots Section 6.3.2: Added individual concentrations (and removed quartiles) to median concentration plots Section 6.3.4: Removed absolute summary and plot. Added summaries and plots for % change from baseline body weight; Additional analysis of body weight change from baseline Section 6.3.5: Added change from baseline figures for select PROs [REDACTED] Section 6.5.1: Added clarification on baseline data for summary Appendix 5: Added example SAS code for additional body weight analysis [REDACTED]
4 16 Mar 2022	N/A	Additional PRO analysis required for clinical development	
 Section 3.3.3: Corrected formatting Sections 3.3.4.5 and 6.3.5.5: Added FAACT-5IASS calculation and analysis Appendix 3: Additional dataset specified

[figure not shown]
2. INTRODUCTION

This statistical analysis plan (SAP) provides the detailed methodology for summary and statistical analyses of the data collected in Study C3651009. This document may modify the plans outlined in the protocol; however, any major modifications of the primary endpoint definition or its analysis will also be reflected in a protocol amendment.

2.1. Study Objectives, Endpoints, and Estimands

Objectives	Endpoints
Primary:	Primary:

 To characterize the safety and tolerability of repeated subcutaneous administrations of PF-06946860 to participants with NSCLC, pancreatic cancer or colorectal cancer and cachexia. 	
 Incidence of treatment emergent adverse events (AEs and SAEs), safety laboratory tests, vital signs (blood pressure and pulse rate) and standard ECG parameters (heart rate, QT, QTcF, PR and QRS intervals).

Secondary:	Secondary:

 To characterize free and total PK of PF-06946860 administered to participants with NSCLC, pancreatic cancer or colorectal cancer and cachexia. 	
 Serum unbound and total trough concentrations (C_{trough}) of PF-06946860 at Weeks 3, 6, 9, 12, and 15..
Tertiary/Exploratory:	Tertiary/Exploratory:

 To evaluate the immunogenicity profile of PF-06946860 in participants with NSCLC, pancreatic cancer or colorectal cancer and cachexia. 	
 Incidence of ADA and NAb, if applicable.

 To characterize the effect of repeated administrations of PF-06946860 on circulating GDF-15 concentrations in participants with NSCLC, pancreatic cancer or colorectal cancer and cachexia. 	
 Serum concentrations of total and, if feasible, unbound GDF-15 at time points specified in the schedule of activities (SoA) in the protocol.

 To evaluate the effect of PF-06946860 on Lumbar Skeletal Muscle Index (LSMI) measured by CT scan in participants with NSCLC, pancreatic cancer or colorectal cancer and cachexia. 	
 Change from baseline LSMI measured by CT scan at time points specified in the schedule of activities (SoA) in the protocol.

 To evaluate the effect of PF-06946860 on body weight in participants with NSCLC, pancreatic cancer or colorectal cancer and cachexia. 	
 Change from baseline body weight at time points specified in the schedule of activities (SoA) in the protocol.
	
	
	

 Cohort 1 only: To evaluate the effect of PF-06946860 on Patient-Reported Outcomes Version of the Common Terminology Criteria for Adverse Events (PRO-CTCAE) selected items in participants with NSCLC, pancreatic cancer or colorectal cancer and cachexia. 	
 Change from baseline scores for selected PRO-CTCAE items at time points specified in Table 2 in the protocol.

 Cohort 1 only: To evaluate the effect of PF-06946860 on fatigue as measured by the PROMIS-Fatigue questionnaire in participants with NSCLC, pancreatic cancer or colorectal cancer and cachexia. 	
 Change from baseline score for PROMIS-Fatigue at time points specified in Table 2 in the protocol.

 Cohort 1 only: To evaluate the effect of PF-06946860 on physical function as measured by the PROMIS-Physical Function questionnaire in participants with NSCLC, pancreatic cancer or colorectal cancer and cachexia. 	
 Change from baseline score for PROMIS-Physical Function at time points specified in Table 2 in the protocol.

 Cohort 1 only: To evaluate the effect of PF-06946860 on HRQoL as measured by FAACT in participants with NSCLC, pancreatic cancer or colorectal cancer and cachexia. 	
 Change from baseline FAACT total and sub-scale scores at time points specified in Table 2 in the protocol.

 Cohort 1 only: To evaluate the effect of PF-06946860 on Patient Global Impression of Severity (PGI-S) and Patient Global Impression of Change (PGI-C) in participants with NSCLC, pancreatic cancer or colorectal cancer and cachexia. 	
 Change from baseline PGI-S at time points specified in Table 2 in the protocol. PGI-C at time points specified in Table 2 in the protocol.
	
	

 To evaluate the effect of PF-06946860 on ability to complete anti-tumor treatment as originally prescribed in participants with NSCLC, pancreatic cancer or colorectal cancer and cachexia. 	
 Number and % of participants completing anti-tumor treatment as originally prescribed.

 To evaluate the effect of PF-06946860 on participant survival in participants with NSCLC, pancreatic cancer or colorectal cancer and cachexia. 	
 Number and % of participants alive at last subject last visit (LSV).

 To evaluate tumor burden in participants with NSCLC, pancreatic cancer or colorectal cancer and cachexia. 	
 The RECIST 1.1 categorization using CT scan at time points specified in the schedule of activities (SoA) in the protocol.

 To enable exploratory research through collection of banked biospecimens, unless prohibited by local regulations or ethics committee decision. 	
 Potential results from exploratory analysis of banked biospecimens (these results may or may not be generated in the context of the present study).

There are no estimands for this study.

2.2. Study Design

This is a Phase 1b, open-label study in participants with advanced metastatic NSCLC, pancreatic cancer or colorectal cancer and cachexia, and elevated circulating GDF-15 concentrations, that are eligible for treatment with platinum-based systemic anti-tumor therapy. Baseline GDF-15 levels will be assessed at screening to determine eligibility for participation.

Following the 28-day screening period to confirm eligibility, the study will consist of a treatment period of 12 weeks and a follow-up period of 12 weeks. The total duration of participation in this study is approximately 24 weeks (not including the screening period).

During the 12-week treatment period in Cohort 1, participants will receive a total of 5 doses of PF-06946860, administered subcutaneously (SC), every 3 weeks (Q3W).

This study will consist of up to 2 cohorts. In each study cohort, approximately 8 participants will be enrolled such that approximately 6 evaluable participants complete the study. Participants who discontinue prior to completion of the study may be replaced, at the discretion of the investigator and sponsor. It is planned that the 2 cohorts will be enrolled sequentially and will follow similar schedules of activity. The optional Cohort 2 may be conducted at the discretion of the Sponsor, with data emerging from Cohort 1 informing the dose level and/or frequency to be administered in Cohort 2.

3. ENDPOINTS AND BASELINE VARIABLES: DEFINITIONS AND CONVENTIONS

3.1. Primary Endpoint(s)

Incidence of treatment emergent adverse events (AEs and SAEs), safety laboratory tests, vital signs (blood pressure and pulse rate) and standard ECG parameters (heart rate, QT, QTcF, PR and QRS intervals).

3.1.1. Adverse Events

An adverse event is considered a Treatment-Emergent Adverse Event (TEAE) if the event started during the effective duration of treatment. All events that start on or after the first dosing day and time/start time, if collected, but before the last dose plus the lag time will be flagged as TEAEs. The algorithm will not consider any events that started prior to the first dose date.

A 3-tier approach for summarizing AEs will not be used due to the low number of participants planned to be recruited.

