#### Type of Participant and Disease Characteristics:

2. Participants who are willing and able to comply with all scheduled visits, treatment plan, laboratory tests, lifestyle considerations, and other study procedures.
3. Documented histologic or cytologic diagnosis of advanced metastatic NSCLC, advanced/unresectable pancreatic cancer, or metastatic colorectal cancer by American Joint Committee on Cancer (AJCC) criteria
4. Cachexia, defined using Fearon's criteria:
  - Body Mass Index (BMI)  $<20 \text{ kg/m}^2$  with involuntary weight loss of  $>2\%$  within 6 months prior to screening; or
  - Involuntary weight loss of  $>5\%$  within 6 months prior to screening irrespective of BMI; or

If medical record documentation is unavailable, patient's report will suffice to estimate involuntary body weight loss.
5. Serum GDF-15 levels of  $\geq \text{CCI}$  (as measured using the Investigational Use Only Roche Elecsys GDF-15 assay) at screening.

6. Participants considered eligible for systemic anti-cancer treatment/therapy at the time of screening, who:
  - Are diagnosed with advanced metastatic NSCLC who will be treated with:
    - A platinum + pemetrexed  $\pm$  pembrolizumab; or
    - A platinum + nab paclitaxel or paclitaxel  $\pm$  pembrolizumab; or
    - Pembrolizumab alone.
  - Are diagnosed with advanced/unresectable pancreatic cancer who will be treated with:
    - FOLFIRINOX; or
    - Nab-Paclitaxel + Gemcitabine;
    - Gemcitabine.
  - Are diagnosed with metastatic colorectal cancer who will be treated with:
    - FOLFOX +/- Biologic (Bevacizumab or Cetuximab/Panitumumab); or
    - FOLFIRI +/- Biologic (Bevacizumab or Cetuximab/Panitumumab); or
    - FOLFOXIRI +/- Biologic (Bevacizumab or Cetuximab/Panitumumab); or
    - Pembrolizumab for MSI-H.
  - Will be entering the study at the first or second cycle of their current course of anti-cancer treatment/therapy.

Note: Other therapies can be considered upon discussion with the Pfizer medical monitor.

7. Adequate liver function as evidenced by liver enzymes, including:

- Total serum bilirubin  $\leq$ 1.5 x upper limit of normal (ULN) unless the participant has documented Gilbert syndrome;
- Aspartate and Alanine aminotransferase (AST and ALT)  $\leq$ 2.5 x ULN;  $\leq$ 5.0 x ULN if there is liver involvement by the tumor;
- Alkaline phosphatase  $\leq$ 2.5 x ULN ( $\leq$ 5 x ULN in case of bone metastasis).

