### 10.3. Appendix 3: Adverse Events: Definitions and Procedures for Recording, Evaluating, Follow-up, and Reporting

#### 10.3.1. Definition of AE

AE Definition

• An AE is any untoward medical occurrence in a patient or clinical study participant, temporally associated with the use of study intervention, whether or not considered related to the study intervention.

• NOTE: An AE can therefore be any unfavorable and unintended sign (including an abnormal laboratory finding), symptom, or disease (new or exacerbated) temporally associated with the use of study intervention.

Events Meeting the AE Definition

• Any abnormal laboratory test results (hematology, clinical chemistry, or urinalysis) or other safety assessments (eg, ECG, radiological scans, vital sign measurements), including those that worsen from baseline, considered clinically significant in the medical and scientific judgment of the investigator (ie, not related to progression of underlying disease).

• Exacerbation of a chronic or intermittent preexisting condition including either an increase in frequency and/or intensity of the condition.

• New conditions detected or diagnosed after study intervention administration even though it may have been present before the start of the study.

• Signs, symptoms, or the clinical sequelae of a suspected drug-drug interaction.

• Signs, symptoms, or the clinical sequelae of a suspected overdose of either study intervention or a concomitant medication. Overdose per se will not be reported as an AE/SAE unless it is an intentional overdose taken with possible suicidal/self-harming intent. Such overdoses should be reported regardless of sequelae.

Events NOT Meeting the AE Definition

• Any clinically significant abnormal laboratory findings or other abnormal safety assessments which are associated with the underlying disease, unless judged by the investigator to be more severe than expected for the participant's condition.

• The disease/disorder being studied or expected progression, signs, or symptoms of

the disease/disorder being studied, unless more severe than expected for the participant's condition.

- Medical or surgical procedure (eg, endoscopy, appendectomy): the condition that leads to the procedure is the AE.

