#### Follow-up of AEs and SAEs

- The investigator is obligated to perform or arrange for the conduct of supplemental measurements and/or evaluations as medically indicated or as requested by the sponsor to elucidate the nature and/or causality of the AE or SAE as fully as possible. This may include additional laboratory tests or investigations, histopathological examinations, or consultation with other healthcare professionals.
- If a participant dies during participation in the study or during a recognized follow-up period, the investigator will provide Pfizer Safety with a copy of any postmortem findings including histopathology.
- New or updated information will be recorded in the originally completed CRF.
- The investigator will submit any updated SAE data to the sponsor within 24 hours of receipt of the information.

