6. ANALYSES AND SUMMARIES

6.1. Primary Endpoint(s)

6.1.1. Adverse Events

Adverse events will be summarised by treatment and overall and in accordance with sponsor reporting standards using the safety population defined in Section 4.

Incidence and CTCAE grade of treatment emergent adverse event (TEAE) tables will additionally be produced ('All causality' and 'Treatment related', separately) to summarise the total number of adverse events by preferred term, which will be reported by treatment and overall.

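### The SAP's onset-only TEAE rule has no clause for an adverse event already open at first dose that worsens afterwards, so such worsening can drop out of the primary TEAE tables

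*SAP*

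**What the plan says.** The primary endpoint in SAP section 3.1 opens with TEAEs: "Incidence of treatment emergent adverse events (AEs and SAEs), safety laboratory tests, vital signs (blood pressure and pulse rate) and standard ECG parameters". Section 3.1.1 fixes what counts: "An adverse event is considered a Treatment-Emergent Adverse Event (TEAE) if the event started during the effective duration of treatment". It then rules out anything earlier: "The algorithm will not consider any events that started prior to the first dose date". Section 6.1.1 builds its tables on that flag: "Incidence and CTCAE grade of treatment emergent adverse event (TEAE) tables will additionally be produced".

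The protocol bears on this in three places.

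- Section 8.3.1 starts adverse event collection at informed consent, and the Schedule of Activities puts screening at Day -28 to Day -1. Adverse event records can therefore exist before the first dose.
- Section 5.1, criterion 6, describes when participants join relative to chemotherapy: "Will be entering the study at the first or second cycle of their current course of anti-cancer treatment/therapy".
- On worsening, Appendix 3 contains two statements. Section 10.3.1 lists among events that meet the adverse event definition: "Exacerbation of a chronic or intermittent preexisting condition including either an increase in frequency and/or intensity of the condition". Section 10.3.3, under follow-up, says: "New or updated information will be recorded in the originally completed CRF".

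**The concern.** A toxicity of the first chemotherapy cycle, such as nausea or fatigue, may be an open grade 1 or 2 record when a second-cycle entrant receives the first dose of PF-06946860. If it becomes grade 3 afterwards, that change is part of the tolerability picture the study is meant to give. Under a rule that looks only at the start date, the change is invisible unless someone opens a new record for it.

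TEAE incidence is part of the primary endpoint. This is the first use of the drug in patients with cancer and cachexia, there is no control arm, and each cohort has about 8 participants. The same clinical course could be a TEAE at one site and not at another purely because of data entry.

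**Working it through.** The plan states no TEAE rate, alpha, power or effect size, so there is no figure to reproduce. The check is mainly textual, with a short calculation for scale.

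**Step 1. Apply the rule to each kind of record.**

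| Situation | Onset on record | TEAE under SAP 3.1.1? |
|---|---|---|
| A. New event after first dose, within the window | Post-dose | Yes |
| B. Medical-history condition worsens after dosing and is entered as an adverse event | Post-dose | Yes |
| C. Adverse event opened between consent and Day 1 worsens after dosing, entered as a new record | Post-dose | Yes |
| D. As C, but the original record is updated | Pre-dose | No |

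Only D is lost. Protocol 10.3.1 supports B and can be read to support C. Protocol 10.3.3 leaves room for D. Neither says whether a grade increase in an open adverse event starts a new record, and neither mentions the onset date.

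**Step 2. Who can be in C or D.** Anyone with an adverse event starting in the screening period, up to 28 days. For toxicity of the current chemotherapy course this mainly means second-cycle entrants. Protocol 6.1.1 puts PF-06946860 at least 0.5 h before anti-tumor therapy on a shared dosing day, so a first-cycle entrant dosed that day has the toxicities of that course after the first dose.

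**Step 3. Whether another output shows the same event.**

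- Laboratory tests, vital signs and ECG are separate parts of the primary endpoint with their own pre-dose baselines (SAP 3.1.2 to 3.1.4). Worsening anaemia or transaminases is visible there.
- Nausea, vomiting and fatigue have no such second route in the primary endpoint. PRO-CTCAE covers them in Cohort 1 only, and Protocol 8.1.3.2 keeps it separate from the CTCAE events.
- Protocol 9.4.4 makes reporting of adverse events collected at screening optional.
- The planned CTCAE grade tables are TEAE tables, so they inherit the exclusion.

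**Step 4. Scale.** One participant's share of a term's incidence is 100/n:

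- n = 8 (assigned per cohort, Protocol 9.2): 100/8 = 12.5 points
- n = 6 (evaluable completers): 100/6 = 16.7 points

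For the number affected, three shares must be assumed, because the documents give none of them: s = share entering at cycle 2; w = share of those with a pre-dose adverse event that worsens after dosing; u = share of those worsenings kept on the original record. Expected participants affected = n × s × w × u, and P(at least one) = 1 − (1 − s × w × u)^n. With n = 8:

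| s | w | u | Expected | P(at least one) |
|---|---|---|---|---|
| any | any | 0 | 0 | 0 |
| 0.25 | 0.1 | 1 | 8 × 0.025 = 0.2 | 1 − 0.975^8 = 0.18 |
| 0.5 | 0.3 | 0.5 | 8 × 0.075 = 0.6 | 1 − 0.925^8 = 0.46 |
| 1.0 | 0.5 | 1 | 8 × 0.5 = 4.0 | 1 − 0.5^8 = 0.996 |

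The result depends strongly on u, the recording convention, on which the documents are silent.

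**The case against.** The strongest reply is that the protocol already treats an exacerbation as an adverse event in its own right, and that Appendix 3 also tells sites to record worsening signs and symptoms of the malignancy as adverse events. Entered with a post-dose onset, these pass the SAP rule. The sentence about the originally completed CRF sits among general follow-up bullets on extra tests, postmortem findings and SAE updates, and says nothing about grade or onset. This stands, and it rules out the tempting reading that the SAP drops every pre-dose event that worsens. It does not close the gap: for an adverse event already on the CRF, no text tells the site to open a new record.

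It can also be said that TEAE tables are produced in addition to summaries under sponsor reporting standards, that monthly safety reviews cover all available data, that SAE reporting does not depend on the TEAE flag, and that SAP 5.1 has no decision rule that could flip. All of that is fair. It lowers the stakes but leaves the TEAE component of the primary endpoint dependent on an unstated convention.

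A reader might also object to the end of the window, "but before the last dose plus the lag time will be flagged as TEAEs", because no lag value is given. That is missing detail which sponsor standards may supply, and the documents do not show that any particular end date is required. It is not part of this point.

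**Conclusion.** The point holds in a limited form. The rule is onset-only, it expressly excludes events that began before the first dose, and it has no clause for later worsening. An adverse event open at Day 1 that increases in grade or becomes serious after dosing is left out of the TEAE tables if it stays on its original record.

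The size is unknown and starts at zero. Each participant missed lowers a term's incidence by 12.5 points at n = 8. Whatever its size, the error can only reduce the TEAE count.

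A reader might infer that the primary endpoint as a whole understates harm, or that a table would show 0 of 8 where the truth is 1 to 3 of 8. The documents support neither. Laboratory, vital-sign and ECG worsening is assessed separately, and no frequency of worsening or of second-cycle entry is given. The conclusion assumes only that some screening adverse events remain open at Day 1 and that the CRF instructions and sponsor standards, which are not available here, do not already settle the matter. It is a worthwhile low-cost correction and does not call the design into question.

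**What to change.** In SAP 3.1.1, replace the exclusion sentence with: *Events that started before the first dose are treatment-emergent if their CTCAE grade or seriousness increases on or after the first dose.*

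Add one CRF completion instruction: a post-dose grade increase in an open adverse event is entered as a new record with its own start date or, alternatively, dated grade changes are captured on the existing record. Use one method throughout, so that a worsening is not counted twice where the tables count events. Query records already entered that were open at first dose.

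The cost is one SAP sentence, one site instruction and some queries. The queries may matter, because the rationale for SAP version 3 cites findings during BDRs. That abbreviation is not expanded; if it means data reviews, records already existed by then, and a new instruction alone would not re-date them. The downside is that some chemotherapy-driven worsening will be counted as all-causality TEAEs. The separate treatment-related tables in SAP 6.1.1 help a reader to tell these apart.
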